1. SYNOPSIS

Study Title: A prospective, observational, non-comparative, open-label study to investigate the effectiveness of the treatment with weekly Alendronate in postmenopausal women with Osteoporosis.

Objectives:

The primary objective of this study is to evaluate Bone Mineral Density (BMD) changes at lumbar spine of Greek osteoporotic women from baseline to 12th month from the initiation of Alendronate 70mg once weekly.

The secondary objectives of this study are to estimate new vertebral and non-vertebral fragility fractures, hip fractures, treatment compliance, occurrence of back pain and days lost from work due to fracture related back pain from baseline to 12th month from the initiation of Alendronate 70mg once weekly. Also, to evaluate the safety of Alendronate assessed by the type, frequency, and severity of ADRs for 18 months after the initiation of study.

Design and Outcomes:

This is a Greek observational prospective study of 12 months to evaluate the effect of Alendronate 70mg once weekly on BMD change (%) at lumbar spine in postmenopausal women. The decision to treat the patient with Alendronate must be made independent of and prior to their enrollment in the study. Patients eligible to participate will receive their prescription monthly.

Primary Outcome:

- BMD change (%) at lumbar spine at 6,12 months of treatment measured by DXA

Secondary Outcomes:

- the proportion of patients with severe osteoporosis experiencing one or more new vertebral and non-vertebral fragility fractures assessed by spine radiographs regardless of symptoms
- Compliance to therapy, self-reported by patients
- Days lost from work due to fracture-related back pain, self reported by patients

Secondary Safety Outcomes:

- the proportion of patients with ADR to Alendronate
- the proportion of patients with serious ADR to Alendronate

Treatment Procedures and Duration:

Patients will return to the clinic every month to receive their Alendronate 70mg prescription. Patients will be observed for a period of up to 12 months after their entry in the study and will be followed up for 6 months after their last visit.

Sample Size and Population:

Inclusion criteria: Postmenopausal women who are diagnosed with osteoporosis.

Exclusion criteria: Previous treatment with drugs that modify bone metabolism or serious bone/esophageal/renal disease.

Approximately 512 patients need to be enrolled in the study to achieve the desired precision. Patient pool will be the orthopaedic clinic of Larisa Public Hospital.

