6. STUDY DESIGN

This is a Greek observational prospective study to evaluate the effect of a biphosphonate drug, Alendronate, on BMD in postmenopausal women for a total period of 12 months. This observational study will not alter the routine clinical management of patients and will comply with all applicable local regulations of Greece. The decision to treat the patient with Alendronate must be made independent of and prior to their enrollment in the study. It is expected that patients eligible to participate will receive their first prescription during their initial clinic appointment and thereafter once monthly along with local standard clinical care according to clinical judgment and international guidelines. Approximately 512 patients will be enrolled in the study. The first 512 patients that will attend the orthopaedic clinic of Larisa Public Hospital and will be deemed appropriate candidates for biphosphonates treatment will be eligible to participate in the study. Detailed data obtained as part of routine clinical practice will be collected at the initial visit directly from patients or through their past medical record. These will comprise of demographic patient data, medical condition, risk factors for osteoporosis, and comorbidities. It is anticipated that patients will return to the clinic every month to receive their Alendronate prescription and record protocol adherence. After the initial visit, information regarding Alendronate prescription and administration, concomitant medication use, and non-serious and serious ADRs will be obtained during monthly clinical visits and recorded for up to approximately 6 months after completion of the study, a period that is thought appropriate to document ADRs and serious ADRs.

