10. STATISTICAL CONSIDERATIONS

Study Outcomes:

The following outcomes are to characterize/estimate the effectiveness during the first 12 months of treatment with Alendronate.

Primary outcome:

- BMD change (%) at lumbar spine at 6,12 months of treatment measured by DXA

Secondary outcomes:

- the proportion of patients with severe osteoporosis experiencing one or more new vertebral and non-vertebral fragility fractures assessed by spine radiographs regardless of symptoms
- Compliance to therapy, self-reported by patients
- Days lost from work due to fracture-related back pain, self reported by patients

The following secondary outcomes are to characterize the safety of patients during the first 12 months of treatment with Alendronate and during the 6 month follow up period:

- the proportion of patients with ADR to Alendronate
- the proportion of patients with serious ADR to Alendronate

The Full Analysis Set will consist of all enrolled patients satisfying the inclusion/exclusion criteria that receive at least 46 doses - 96% of the 48 that ideally would receive during the study duration- and have a non-missing enrollment date. All analyses will be performed on this analysis set.

Subsets and/or Covariates:

The following variables will be collected at baseline, either directly as part of routine clinical practice, or from medical records when available:

Demographic patient data:

- Educational level
- Patient employment status
- Patient living situation (at home with spouse/family, at home with care/support, at home alone, nursing home)

Medical condition regarding osteoporosis:

- Body mass index (≤ 25 or > 25 kg/m²)
- Age at menopause
- Cause of menopause (natural onset, clinically/surgically induced)
- Height loss since maximal height
- Height loss in centimeters (cm)
- Previous fracture
 - Previous hip fracture
 - Previous vertebral fracture
 - Other previous fractures
- Previous hospitalization for osteoporotic fracture and/or surgical osteoporotic fracture treatment
- One or more falls experienced during the past 12 months
- One or more episodes of immobility experienced during the past 12 months
- Parent fractured hip
- Current smoker
- Former smoker
- Systemic glucocorticoid use
- Secondary osteoporosis
- Alcohol consumption
- Femoral neck BMD T-score
- Lumbar spine BMD T-score
- Total hip BMD T-score

Patient-related:

- Age (years)
- Age group (< 65, ≥ 65 to <75, ≥ 75 years)
- Time since Post Menopausal Osteoporosis (PMO) diagnosis

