- Number of comorbidities
- Any chronic medical condition
- Type of chronic medical condition (diabetes/osteoporosis/hypertension/other)

Sample Size:

A review of published data highlighted that BMD change at lumbar spine at 12 months for postmenopausal women on alendronate 70mg weekly ranges from 3.7%-5.1%.¹³⁻¹⁵

Taking into account the most unfavourable result, which is 5.1%, we will estimate the sample size of our study. We will conduct an observational study which intends to investigate the Lumbar Spine BMD (%) change from baseline to 12 months (single proportion).

Published data estimate that Lumbar Spine BMD increases 5.1% from baseline to 12 months.

We would like to ensure that 95% CI of the Lumbar Spine BMD change (%) is estimated with precision ±2% (i.e. with a margin of error of 2%).

The required sample size would be $n \geq \frac{z^2}{\delta^2} p(1-p) \rightarrow n \geq \frac{1.96^2}{0.02^2} 0.051(1-0.051) \rightarrow n \geq 465$

If we add 10% to compensate for potential loss of subjects, the final number will sum up to $n \geq 512$ patients.

Thus in order to have sufficient precision and compensate for potential loss of subjects the final sample size should be 512 patients.

Data Analyses

This is an observational study for which the analysis will be descriptive in nature and no formal hypothesis will be tested. T test will be used to assess the change in BMD between baseline and end of study measurements. Significance was indicated at $P < 0.05$.

For quantitative parameters (BMD, days lost from work) mean, standard deviation, median, range (minimum and maximum), as well as number of missing data (if relevant) will be displayed. For qualitative parameters (bone fractures) counts, percentages and number of missing data if relevant will be displayed. Treatment compliance for each patient will be calculated as the number of doses study drug was actually taken, with the maximum count being 48. Compliance will be regarded as a quantitative parameter.

In general, missing values will remain as missing, i.e., no attempt will be made to impute missing values and only observed values will be used in data analyses and presentations.

Baseline characteristics will be described. Demographics, medical history and other baseline variables will be summarized as appropriate to the type of data.

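### Compliance rests on self-report alone and is summarised only in women with at least 46 of 48 doses, so it can hardly vary and over-reporting cannot be gauged, although prescription records are collected

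*Protocol*

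**What the plan says.** The synopsis and Section 10 of the protocol both list the secondary outcome as "Compliance to therapy, self-reported by patients". Section 10 (Data Analyses) defines the score as "calculated as the number of doses study drug was actually taken, with the maximum count being 48" and adds: "Compliance will be regarded as a quantitative parameter". The maximum is the same for every woman.

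Section 10 also defines the Full Analysis Set. Besides meeting the eligibility criteria and having an enrolment date, a woman must "receive at least 46 doses", which the protocol gives as 96% of 48. Every analysis is to use this set, and compliance is not exempted.

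Supply data are collected as well. Section 6 anticipates that "patients will return to the clinic every month to receive their Alendronate prescription and record protocol adherence" and states that "information regarding Alendronate prescription and administration, concomitant medication use, and non-serious and serious ADRs will be obtained during monthly clinical visits". The table in Section 14 records the alendronate prescription at enrolment, in the observation period and at end of study. The protocol does not link these records to the compliance score.

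**The concern.** There are two weaknesses, and they compound each other.

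First, the analysis set is selected on the quantity being described. A compliance summary restricted to women who have already reached 46 of 48 doses says almost nothing about compliance in Greek women starting weekly alendronate. Those who stopped early or took the drug irregularly are left out.

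Second, the score is worded as doses actually taken, but its only named source is the woman's own report, and its only stated limit is the common maximum of 48. A woman with gaps in her prescriptions can report a full count and be scored as fully compliant. The prescription record could show how often report and supply disagree, but the plan makes no such comparison.

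The point may also reach the primary outcome. The protocol does not say which dose count drives the 46-dose rule, and the only count it defines is the compliance score. If that is the count used, a reporting error of one to three doses can decide whether a woman enters the BMD analysis.

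**Working it through.** **Inputs.** From Section 10: maximum count 48, threshold 46. From Sections 1 and 6: monthly prescriptions, so about 12 in 12 months. Tablets per prescription are not stated, so a range is used.

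**1. The plan's own figure.** 46/48 = 0.958, which rounds to the stated 96%. It reproduces.

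**2. Range of the outcome in the analysis set.** If the compliance count is also the count behind the 46-dose rule, the possible values are 46, 47 and 48:

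- 46/48 = 95.8%
- 47/48 = 97.9%
- 48/48 = 100%

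The mean must lie between 46 and 48. The standard deviation cannot exceed half the range, (48 − 46)/2 = 1 dose. These limits follow from the selection rule, whatever the women do.

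**3. What a prescription record could show.** Doses covered = number of prescriptions × tablets per prescription.

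| Tablets per prescription (assumed) | 12 prescriptions | 11 | 10 | 9 |
|---|---|---|---|---|
| 48/12 = 4 | 48 | 44 | 40 | 36 |
| 52/12 = 4.33 | 52 | 47.7 | 43.3 | 39 |
| 5 | 60 | 55 | 50 | 45 |

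At 4 tablets, one missed prescription leaves 44 doses covered, fewer than 46. At 4.33, one missed prescription still covers 46 or 47 doses but not 48, and two leave 43.3. At 5, three must be missed before coverage falls below 46. In each of these cases a report of 48 would still pass the common maximum.

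**4. Effect on mean compliance (illustration).** Suppose a share f of all women miss one four-tablet prescription but report 48. Overstatement of the mean = 4 × f doses, or 100 × 4f/48 percentage points.

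- f = 5%: 0.2 doses, 0.4 points
- f = 10%: 0.4 doses, 0.8 points
- f = 20%: 0.8 doses, 1.7 points
- f = 30%: 1.2 doses, 2.5 points

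**5. Sensitivity of the 46-dose threshold (illustration).** With X ~ Binomial(48, p) and independent doses, P(X ≥ 46) is the sum of the probabilities of 46, 47 and 48.

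| p | P(X ≥ 46) |
|---|---|
| 0.90 | 0.129 |
| 0.93 | 0.338 |
| 0.95 | 0.567 |
| 0.96 | 0.699 |

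If true per-dose adherence were 90% but reports ran at 95%, the share reaching 46 would appear to be 57% instead of 13%. With 93% true and 96% reported, it would be 70% instead of 34%. These rates are assumed. Independence is also a simplification, since a missed prescription removes doses in a block. The calculation shows only that a threshold two doses below the maximum is sensitive to small reporting errors.

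**The case against.** The protocol openly labels the outcome as self-reported and claims no objective measure. None of its figures on this point is wrong. A supportive prescription-based measure could sit in an analysis plan that is not shown. All of that is fair, but the protocol itself fixes the source, the common maximum and the restriction of every analysis to women with at least 46 doses. Those choices can be reviewed as they stand.

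A reader might infer that compliance is shown to be biased upward and that impossible counts would go unnoticed. The documents support neither. They give no evidence on the direction or size of reporting error. Section 13 requires investigators to verify the consistency of the case report forms and gives them access to medical records. What is missing is narrower: a stated limit specific to each woman, and a rule for resolving a conflict between report and supply.

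A reader might also infer that each count should be capped at prescribed doses and the capped count used for the 46-dose rule. That goes too far. Monthly return is only anticipated, the drug is not supplied by the study, and tablets per prescription are not given. Prescriptions obtained elsewhere would be missed, so compliant women could be removed from every analysis, including primary BMD. A prescription is also proof of neither dispensing nor intake.

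Finally, the rule speaks of doses received, which could mean prescribed doses. On that reading the self-reported count is not strictly confined to 46 to 48, and prescription data already play a part. The summary would still omit every woman who received fewer than 46 doses.

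**Conclusion.** The point holds as a weakness of measurement and of analysis population, not as a demonstrated bias. As written, compliance will be described by self-report alone, in a set chosen for near-complete dosing. Provided the rule and the outcome use the same dose count, the result must fall between 95.8% and 100%. The plan also gives no means of gauging over-reporting, although the supply data are collected.

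Of the two weaknesses, the restriction to at least 46 doses is the larger. Comparing reports with prescriptions would not cure it; compliance has to be summarised in all women who start treatment.

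The 44-dose example depends on four tablets per prescription. The shifts in the mean (0.2 to 1.2 doses) and the binomial probabilities depend on assumed shares and rates. None of them estimates bias in this study. The change should be made, because compliance is a stated objective and the remedy is cheap.

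**What to change.** In Section 10 of the protocol:

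1. Summarise the self-reported dose count in all women who start alendronate, not only in the Full Analysis Set.
2. Beside it, report prescription coverage: doses covered by recorded prescriptions, divided by weekly doses due from first prescription to month 12, using the supply recorded for each prescription. State the denominator, since 12 months of 4 weeks gives 48 and a 52-week year gives 52.
3. Flag and query any self-reported count above the recorded supply, and report how many women are affected.
4. Use a prescription-capped count only as a sensitivity analysis of compliance, not to decide entry to the analysis set.
5. State which dose count the 46-dose rule uses.

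The cost is protocol and analysis-plan wording, one derived variable and a data query. No clinical procedure is added, which fits the limit in Section 8. It does require the tablets per prescription to be recorded on the case report form, which the protocol does not say. The drawback is that prescriptions obtained outside the clinic are missed and a prescription does not prove intake. For that reason the two measures are shown side by side and neither replaces the other.

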3. LIST OF ABBREVIATIONS

ADR	Adverse Drug Reaction
BMD	Bone Mineral Density
BMI	Body Mass Index
DXA	dual energy X-ray absorptiometry
EC	Ethics Committee
ECG	Electrocardiogram
eCRF	electronic Case Report Form
EOF	National Organization for Medicines
IRB	Institutional Review Board
PMO	Post Menopausal Osteoporosis
SADR	Serious Adverse Drug Reaction
SID	Study Identification Number
WHO	World Health Organization

4. STUDY OBJECTIVES

Primary objective:

Evaluate Bone Mineral Density (BMD) changes at lumbar spine of Greek osteoporotic women from baseline to 12th month from the initiation of Alendronate 70mg once weekly.

Secondary objectives:

Evaluate new vertebral and non-vertebral fragility fractures, hip fractures, treatment compliance, occurrence of back pain and days lost from work due to fracture related back pain from baseline to 12th month from the initiation of Alendronate 70mg once weekly.

Also evaluate the safety of Alendronate assessed by the type, frequency, and severity of ADRs for 18 months after the initiation of study.

5. BACKGROUND

Disease

Osteoporosis is described by the World Health Organization as a 'progressive systemic skeletal disease characterized by low bone mass and microarchitectural deterioration of bone tissue, with a consequent increase in bone fragility and susceptibility to fracture.'¹ Osteoporosis is a major public health threat; in a recent review, the prevalence of osteoporosis was reported as an estimated 200 million people worldwide while about 40 to 50% of women are at risk of having an osteoporotic fracture in their lifetimes.^{2,3}

Nonetheless, most women with osteoporosis remain asymptomatic, which makes epidemiological research especially difficult.⁴ Osteoporosis related fractures are associated with significant morbidity and mortality. Their non-fatal consequences include pain, physical impairment and loss of functional ability, which can have significant adverse effects on patient quality of life. There are also substantial costs to society in terms of diminished activity, hospitalization and lengthy stays in nursing homes as well as days lost from work.⁵

A diagnosis of osteoporosis can be made on the base of either fractures occurring without significant trauma or low bone mineral density measured by dual energy X-ray absorptiometry (DXA).⁶

According to the WHO diagnostic classification, osteoporosis in Caucasian women is defined as a bone mineral density (BMD) at the hip or lumbar spine that lies 2.5 standard deviations or more below the average for the young healthy female population (T-score <-2.5 S.D.).⁶ Osteoporosis can be treated effectively mainly by antiresorptive agents, such as bisphosphonates, by anabolic agents, such as parathyroid hormone analogues, by denosumab which is a fully human monoclonal antibody that inhibits RANKL, by strontium, and by raloxifen a selective estrogen receptor modulator.^{7,8} Other non-pharmacological strategies suggested

to reduce the burden of osteoporosis are smoking cessation and exercise.⁹ Bisphosphonates represent a major advance in osteoporosis treatment and remain at the forefront of medications used for years with great efficacy and safety for the care of patients.¹⁰

Drug background

Alendronate is a bisphosphonate that inhibits osteoclastic bone resorption with no direct effect on bone formation. Preclinical studies have shown preferential localization of Alendronate to sites of active resorption. Activity of osteoclasts is inhibited, but recruitment or attachment of osteoclasts is not affected. The bone formed during treatment with Alendronate is of normal quality.¹¹

Alendronate is approved for the prevention (5 mg daily and 35 mg weekly tablets) and treatment (10 mg daily tablet, 70 mg weekly tablet) of postmenopausal osteoporosis. Alendronate is also approved for treatment to increase bone mass in men with osteoporosis and for the treatment of osteoporosis in men and women taking glucocorticoids.¹ In the initial efficacy studies of Alendronate, the mean bone mineral density (BMD) increases with Alendronate 10 mg/day relative to placebo at three years with 8.8%, 5.9% and 7.8% at the spine, femoral neck and trochanter, respectively. Total body BMD also increased significantly. Also, Alendronate reduces the incidence of spine and hip fractures by about 50 percent over three years in patients with a prior vertebral fracture or in patients who have osteoporosis at the hip site. It reduces the incidence of vertebral fractures by 48 percent over three years in patients without a prior vertebral fracture.¹²

Rationale

Even though regulatory approval has been granted for Alendronate many years ago, no large observational study has been conducted in Greek population to collect information on patient characteristics including demographics, comorbid conditions and use of concomitant medications and thus ensure that the drug is being used in patients that it was intended to. Moreover, findings of such a study will help describe women receiving Alendronate for osteoporosis in Greece highlighting at the same time the factors determining therapeutic choice and the patient's fracture risk; comorbid conditions influencing bone health (including systemic, metabolic, rheumatic, thyroid, parathyroid, renal and lung); clinical factors related to osteoporosis (prior fracture, age, ambulatory status, bone turnover markers, BMD T-score, body mass index, Ca (calcium) and vitamin D intake; lifestyle factors (smoking, alcohol and drug use/abuse); and socioeconomic status (employed, retired). In addition, Alendronate efficacy will be confirmed in Greek population.

6. STUDY DESIGN

This is a Greek observational prospective study to evaluate the effect of a biphosphonate drug, Alendronate, on BMD in postmenopausal women for a total period of 12 months. This observational study will not alter the routine clinical management of patients and will comply with all applicable local regulations of Greece. The decision to treat the patient with Alendronate must be made independent of and prior to their enrollment in the study. It is expected that patients eligible to participate will receive their first prescription during their initial clinic appointment and thereafter once monthly along with local standard clinical care according to clinical judgment and international guidelines. Approximately 512 patients will be enrolled in the study. The first 512 patients that will attend the orthopaedic clinic of Larisa Public Hospital and will be deemed appropriate candidates for biphosphonates treatment will be eligible to participate in the study. Detailed data obtained as part of routine clinical practice will be collected at the initial visit directly from patients or through their past medical record. These will comprise of demographic patient data, medical condition, risk factors for osteoporosis, and comorbidities. It is anticipated that patients will return to the clinic every month to receive their Alendronate prescription and record protocol adherence. After the initial visit, information regarding Alendronate prescription and administration, concomitant medication use, and non-serious and serious ADRs will be obtained during monthly clinical visits and recorded for up to approximately 6 months after completion of the study, a period that is thought appropriate to document ADRs and serious ADRs.

